4.4 ADHERENCE AND COMPLIANCE

The planed analysis for Trial Adherence was to investigate the effect of treatment adherence using complier average causal effect (CACE) estimation methods. Intention To Treat (ITT) analysis does not represent treatment effect under non-compliance of treatment, we therefore planned to use CACE analysis to explore whether treatment effect is directly affected by the level of compliance. However, due to the small sample size the above analysis is not appropriate, therefore, compliance and adherence will be reported descriptively as both a dichotomous and continuous variable. The dichotomous: whether the participant took medication at a dose of 100mg or more without interruption during the six months prior to the final follow-up interview; b) Continuous - percentage of medication the participant took in the month prior to competing the six month follow up assessment using data from the Brief Adherence Rating Scale.

This will be presented overall and split by treatment group, continuous variables will be reported with mean values, standard deviations and ranges. Categorical variables will be presented with counts and percentages.

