4.6 MISSING DATA

Missing observations are expected within the dataset. Completion rates of outcome measures will be summarised in the final analysis report, at the item and overall level.

Missing data – outcome item level

For missing items within an outcome measure, the published rules for completing missing data for the relevant measure will be applied. Where there are no missing data rules for the measure, if the number of missing items on an outcome measure is 20% or less, then the missing value for the item will be substituted by the individual's mean score for the remaining items on the scale (Bono, Ried, Kimberlin and Vogel 2007). If there are more than 20% missing items in the scale the outcome measure will not be calculated for the participant at that time point.

Missing data -outcome total score level

A missing completely at random test devised by Little (1998) will be performed to assess whether the data is missing completely at random (MCAR). If this test indicates that data is missing completely at random than analyses will be based on complete cases, else independent t-tests will be conducted to investigate whether the data is missing at random (MAR). If these tests suggest that the missing data is MAR, then predictive mean matching multiple imputation method will be employed. Otherwise, additional modelling guided by clinical knowledge would be required to simulate the missing data mechanism and impute the missing data.

Analysis will be conducted using multiple imputation for the primary and secondary analysis outcome measures. Complete case analysis will be conducted as sensitivity analysis (see section 6.10) to check the impacts that missing data may have had on the results, this is especially important given the small sample and high withdrawal (in relation to the sample) rate.

For imputation, predictive mean matching multiple imputation methods will be adopted. For multiple imputations, the number of imputations completed is dependent upon the percentage of missing data (White, Royston, & Wood, 2011). The current dataset has 18% of the primary outcome missing, which would require 18 imputation sets, which is very large given the total study sample, therefore, the number of imputations with this sample will be limited to m=5, White (2011) state that "Standard texts on multiple imputation suggest that small numbers of imputed data sets (m =3 or 5) are adequate".

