The missing outcome measures will be imputed using group allocation, stratification variables, outcome measure baseline scores and any other baseline characteristics that are deemed to be predictors of missingness. Baseline characteristics will be assessed for being predictors of missingness by running statistical tests on completers versus non completers and evaluating if any differences are present between the two. Baseline factors to be assessed as predictors of missingness include; sex at birth, centre, ward type, ethnicity, Gender (self-identified) and baseline ZAN-BPD scores.

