5.1 TIME POINTS OF OUTCOMES MEASURES

Table 2 below details a list of the outcome measures being collected in the study and at which time points.

Assessments	Screening	Baseline	3-	6-	12 and 18-	Analysis
			month	month	month	
Structured Clinical Interview for Axis II Personality Disorders (SCID-II)	Х	-	-	-	-	Screening tool only - not being presented or analysed
Psychosis Screening Questionnaire	Х	-	-	-	-	Screening tool only - not being presented or analysed
International Personality Disorder Examination (IPDE)	Х	-	-	-	-	Screening tool only - being presented descriptively but not being analysed
Standardised Assessment of Severity of Personality Disorder (SASPD)	-	Х	-	Х	-	GLM analysis at 6 months
Zanarini rating scale for Borderline Personality Disorder (ZAN-BPD)	-	Х	Х	*Х	-	GLM analysis at 3 and 6 months
Brief Psychiatric Rating Scale (BPRS)	-	Х	Х	Х	-	GLM analysis at 3 and 6 months
Acts of Deliberate Self Harm Inventory	-	Х	Х	х	-	To be presented descriptively (count data) at each time point
Modified Overt-Aggression Scale (MOAS)	-	Х	Х	Х	-	GLM analysis at 3 and 6 months
EuroQoL EQ-5D 3 level	-	Х	Х	Х	-	For health economic analysis (being conducted as separate analysis)
The Antipsychotic Non-Neurological Side Effects Scale (ANNSERS)	-	Х	Х	Х	-	GLM analysis at 3 and 6 months
The Extrapyramidal Side Effects Scale	-	Х	Х	Х		GLM analysis at 3 and 6 months
Brief Adherence Rating Scale (BARS)	-		Х	Х	-	T-test at 3 and 6 months
Adult Service Use Schedule (ADSUS) Use of inpatient and community mental health services	-	Х	Х	Х	Х	For health economic analysis (being conducted as separate analysis)
Trial Arm allocation guess				Х		Independent variable for sensitivity analysis - not being used as an outcome measure.

*Primary outcome is Zan-BPD at 6 months.

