5.2 DEFINITIONS AND CALCULATIONS OF OUTCOME MEASURES

The below list indicates the primary and secondary outcomes for the study.

Primary outcome

1. The primary outcome is total score on the Zanarini rating scale for Borderline Personality Disord er (ZAN-BPD) at six months.

Secondary outcomes

- 2. Total score on the Zanarini rating scale for Borderline Personality Disorder at three months.
- 3. General mental health using the Brief Psychiatric Rating Scale (BPRS) at three and six months.
- 4. Incidence and severity of suicidal behaviour using the Acts of Deliberate Self-Harm Inventory.
- 5. Level of aggressive behaviour using the Modified Overt Aggression Scale
- 6. Health related quality of life using the EQ-5D-5L.
- Side effects of medication using the Antipsychotic Non-Neurological Side Effects Scale (ANNSERS) and motor and extrapyramidal side effects using the Extrapyramidal Side Effects Scale.
- 8. Incidence of withdrawal of trial medication due to adverse effects.
- 9. Medication adherence at three and six months using the Brief Adherence Rating Scale.
- 10. Resource use collected using a modified version of the Adult Service Use Schedule and by examining clinical records at six, 12 and 18 months, This will include detailed information about length of inpatient treatment and type of ward (high, medium, low secure, Psychiatric Intensive Care, general adult etc.), contacts with community mental health services and emergency medical services, and the type and dose of psychotropic medication that people are prescribed.

For each measure, its associated analysis to be conducted is listed in table 2. Appendix 1 contains details and definitions of scoring these measures where applicable.

As detailed in the table, the SCID-II, Psychosis screening questionnaire and the IPDE are measures all used for screening and will not analysed. The IPDE will be used to describe the personality profile of the participants. The EQ-5D-3L and ADSUS are being collected for health economic analysis, which will be analysed and reported separately and summarised in a separate health economics analysis plan (HEAP). Additionally, physical health measures for participants are collected on a weekly basis as part

of physical and safety monitoring, these measures will not be summarised or presented as part of the analysis covered in this SAP, we will report on adverse events (see section 5.3 below).

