6.8 ANALYSIS OF SECONDARY OUTCOMES

All secondary outcome measures are continuous measures and will be analysed as the primary outcome model with a GLM to assess the differences between the means of the treatment groups. The baseline measure scores of the associated outcome will be included in the models as covariates to account for the baseline scores. The BARS measure was not applicable at baseline, therefore independent t-test models will be run on that measure at 3 and 6 months.

Secondary outcomes include the ZAN-BPD at 3 months, and all other secondary measures (listed in table 2) at 3 and 6 months (other than the screening tools and health economic measures).

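### Section 4.6 imputes missing adherence (BARS) with a model that ignores stopping of trial medication, so a known 0% can be replaced by the adherence of those still taking it

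*SAP*

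**What the plan says.** **BARS as an outcome.** Section 5.2 lists as secondary outcome 9: "Medication adherence at three and six months using the Brief Adherence Rating Scale". Appendix 1 takes the final score from a 0–100% visual analogue rating and found no missing-value rule for the scale. Section 4.4 uses BARS for the share of medication taken in the month before the six-month assessment.

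**Missing totals (Section 4.6).** The general rule is: "Analysis will be conducted using multiple imputation for the primary and secondary analysis outcome measures". The method is: "For imputation, predictive mean matching multiple imputation methods will be adopted". The predictors are given as: "The missing outcome measures will be imputed using group allocation, stratification variables, outcome measure baseline scores and any other baseline characteristics" that are judged to predict missingness. The candidates named for that last group are all baseline factors.

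The same section also gives a conditional route: "If this test indicates that data is missing completely at random than analyses will be based on complete cases". Predictive mean matching follows if the data look missing at random, and unspecified further modelling otherwise. Section 6.10 adds a complete-case sensitivity analysis of the primary and secondary models.

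**Who is analysed.** Section 4.8 keeps everyone who took at least one dose in the modified ITT set, so later stoppers remain. Section 6.8 notes that BARS has no baseline value.

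**How adherence is reported.** Section 4.4, having dropped the CACE analysis because of the small sample, says "compliance and adherence will be reported descriptively as both a dichotomous and continuous variable". Section 6.8 says "independent t-test models will be run on that measure at 3 and 6 months", and Table 2 in Section 5.1 has "T-test at 3 and 6 months".

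**The concern.** Imputation suits a value that exists but was not observed. For a participant who had stopped trial medication before the rated month, the share of trial medication taken is not unknown. It is 0%. If the BARS form was left blank because there was nothing to rate, the rule in Section 4.6 treats that known zero as missing and fills it from other participants.

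With CACE dropped, the adherence summaries are what a reader will use to judge whether an inconclusive result reflects the drug or the fact that it was not taken. An error here also tends to be larger in the arm with more stopping, which is where a difference between arms would appear. With 29 participants randomised, a few such values move an arm mean noticeably.

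A smaller point is that Section 4.4 gives a descriptive treatment of six-month BARS on small-sample grounds, while Section 6.8 and Table 2 test it. The SAP does not say how the two fit together.

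**Working it through.** The SAP states no figure for BARS missingness or for stopping, so there is no planned figure to reproduce. The check follows the rule through and then illustrates it.

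**1. What the model can know.** Stopping occurs after randomisation and is not among the predictors. There is no baseline BARS to help. Two participants in the same arm with the same baseline data therefore get the same predicted adherence, whether or not one has stopped.

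**2. What is filled in.** Predictive mean matching returns observed donor values. If stoppers are mostly blank, the donors are mostly takers.

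**3. What the other branch does.** A complete-case analysis removes the blank stoppers, so the arm mean becomes the mean of those rated.

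**4. Formula.** Take an arm of size n with s stoppers, all with blank BARS, and mean A among takers.
- Mean with stoppers at 0%: A × (n − s)/n.
- Complete-case mean: A. Imputed mean: about A.
- Overstatement: about A × s/n.

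**5. Illustration. All inputs are assumptions.** n = 14 per arm, close to the 29 randomised. Five blanks in total, borrowed from the 18% missing that Section 4.6 gives for the primary outcome: 5/28 = 17.9%. The SAP does not state that denominator (4/22 = 18.2% fits as well), and the figure is not for BARS. All five blanks are stoppers. A is the same in both arms.

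The imputation was simulated with 500 trials per scenario, SD 15, scores capped at 0–100, five donors, m = 5, and allocation and one baseline variable as predictors. For A = 80:

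| Stoppers per arm | Formula, stoppers at 0% | Simulated, stoppers at 0% | Simulated, imputed |
|---|---|---|---|
| 2 v 3 | 80×12/14 = 68.6 v 80×11/14 = 62.9 | 67.9 v 62.4 | 79.2 v 79.4 |
| 1 v 4 | 80×13/14 = 74.3 v 80×10/14 = 57.1 | 73.6 v 56.5 | 79.3 v 79.0 |
| 0 v 5 | 80.0 v 80×9/14 = 51.4 | 79.5 v 50.9 | 79.5 v 79.3 |

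The simulated means are slightly below the formula because scores are capped at 100. Over A = 60, 80 and 90, the between-arm difference with stoppers at 0% runs from 51.2 − 47.0 = 4.2 to 87.6 − 56.6 = 31.0 points. After imputation it is never more than 0.4.

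**6. Dependence on the key assumption.** If only b of the s stoppers are blank and the rest are rated 0, the complete-case mean is A × (n − s)/(n − b). With A = 80, n = 14, s = 4:
- b = 0: 80×10/14 = 57.1, no overstatement.
- b = 2: 80×10/12 = 66.7, overstated by 9.5.
- b = 4: 80×10/10 = 80.0, overstated by 22.9.

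Rated zeros also join the donor pool, which reduces the error under imputation.

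**7. Section 4.4 against Section 6.8.** The overlap is BARS at six months. Section 4.4 lists means, SDs and ranges and no test. Section 6.8 and Table 2 agree with each other on t-tests at both visits. The two are compatible only if the tests are meant to be additional, which is not stated.

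**The case against.** The strongest reply is that nothing in the SAP says BARS is blank for people who stopped. The scale runs down to 0, and Section 6.10 expects some participants to discontinue medication and stay in the trial. A stopper who is assessed can be rated 0, and then nothing is imputed. This stands. It makes the harm possible rather than certain, and a reader who infers that adherence will be overstated goes further than the document allows.

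Second, Section 4.6 is not a flat rule. It has a complete-case branch and a branch for clinically guided modelling, and Section 6.10 adds a complete-case check. This is true, but it does not rescue the result. Complete cases omit the same stoppers, and the modelling branch is unspecified.

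Third, the adherence picture does not rest on BARS alone. The dichotomous measure in Section 4.4 requires uninterrupted use over the six months, so it classes a stopper as non-adherent. Withdrawal for adverse effects is secondary outcome 8. Discontinuation and its timing are reported under Sections 6.5 and 6.10. These would partly expose a difference in stopping, so it would be wrong to infer that such a difference would go unseen. The exposure is confined to the continuous measure and its t-tests.

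Fourth, a reader might infer that Section 4.4 forbids testing adherence. It does not: it never limits itself to description, and the SAP elsewhere both describes and tests secondary outcomes. What remains is an ambiguity, and removing the t-tests is a matter of preference.

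**Conclusion.** The point holds in a conditional form. The stated rule covers BARS, its predictors carry no information on stopping, and no provision says how adherence is scored once trial medication has stopped. For any participant whose BARS is blank because of stopping or withdrawal, imputation replaces a known 0% with a value drawn mainly from takers, and complete-case analysis drops that participant. Both push continuous adherence upward and can hide a between-arm difference.

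The size cannot be determined from the SAP. Under the assumptions in the working, differences of about 4 to 31 points shrink to about zero. If every stopper was followed up and rated 0, there is no error. The illustration shows what the rule permits and is not an estimate for this trial.

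This concerns a secondary outcome and leaves the primary analysis untouched. The correction is nearly free and should be made before adherence is analysed. The relation between Section 4.4 and Section 6.8 with Table 2 needs only a clarifying sentence.

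**What to change.** - **Section 4.6:** exempt BARS from multiple imputation.
- **Sections 4.4 and 6.8:** set continuous adherence to 0% at any visit where recorded dates show that trial medication had stopped before the rated month. Leave every other missing BARS value as missing and report how many there are, by arm.
- **Reporting:** give by arm the number still taking trial medication at 3 and 6 months, with BARS summarised among them. Stopping and incomplete adherence can then be read separately.
- **Sections 4.4, 6.8 and Table 2:** state whether the t-tests are additional to the descriptive summary. Deleting them is optional.

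The cost is a change of SAP wording and a small derivation step. No new data are needed, because Section 6.10 already requires the time of discontinuation. The downside is that reported adherence becomes less favourable.

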2. STATISTICAL ANALYSIS PLAN AUTHORSHIP

This SAP has been authored by [name] (Senior Statistician NWORTH CTU), Trial Statistician for the CALMED Trial, with input from [name], Senior Trial Statistician for the trial (Principal Statistician NWORTH CTU), [name] (Chief Investigator) and [name] (Trial Manager).

The study began recruitment in September 2019 however, due to several difficulties such as recruiting in this population and the impacts of COVID-19, which are still ongoing, the study struggled to reach recruitment targets. Efforts were made to increase recruitment to the study but unfortunately recruitment to the study remained an issue.

The sample size of the study was re-calculated and reduced, see section 4.1, however in March 2021, with agreement from independent committees and the funder, the study was terminated. At the time of termination, a final sample of 29 randomised patients was reached.

This document details the planned analysis according to the protocol, given the full sample, and the analysis that will be carried out for the study given the sample reached. It should be noted that the sample is very small, and far below the statistical power required to evaluate the intended research question. Therefore, all results presented following the analysis should be interpreted with caution.

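### Section 4.6 cuts the number of imputations from the 18 its own rule gives to 5 because the sample is small. That is not a valid ground, and it adds modest but avoidable noise to the primary estimate.

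*SAP*

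**What the plan says.** SAP Section 4.6 (Missing Data) states its rule first: "the number of imputations completed is dependent upon the percentage of missing data". It then applies the rule to the 18% of the primary outcome that is missing, and sets the result aside in the same sentence: this "would require 18 imputation sets, which is very large given the total study sample". The section concludes that "the number of imputations with this sample will be limited to m=5". As support it cites a general remark, attributed to the same guidance paper as the rule, that small numbers of sets such as 3 or 5 are adequate.

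The method is predictive mean matching ("For imputation, predictive mean matching multiple imputation methods will be adopted"). The imputations are meant to feed the main results: "Analysis will be conducted using multiple imputation for the primary and secondary analysis outcome measures". Complete-case analysis is the sensitivity check, described in Sections 4.6 and 6.10. The sample size referred to is given in Section 2: "a final sample of 29 randomised patients was reached".

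**The concern.** The plan derives a number from its own rule and then overrides it, and the only trial-specific reason is the size of the sample. That reason does not bear on m. Each imputed dataset is another random draw of the same few missing values, so more of them consume no patients, degrees of freedom or information. They only average out the randomness of the draws.

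The supporting remark does not repair this. As the SAP reports it, it is a general statement about what is adequate. It gives no reason why a rule taken from the same paper one clause earlier should give way.

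At stake is the stability of the pooled primary difference from one random seed to another. The comparison of imputed with complete-case results is also affected: the complete-case estimate does not depend on a seed, so all of the seed noise in the imputed estimate passes into the gap between them.

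**Working it through.** **The plan's own figure.** m = 100 × 0.18 = 18. This agrees with Section 4.6.

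**Inputs.**
- From Section 4.1: SD 7.89, target difference 4 points, baseline to follow-up correlation r = 0.3 (range 0.2 to 0.4).
- From Section 4.6: 18% missing, m = 5.
- From Section 2: 29 randomised. The size of the modified intention-to-treat set is not stated. 5/28 = 17.9% and 4/22 = 18.2% both round to 18%, so N = 28 is an assumption and N = 22 to 29 is the range examined.
- Assumed: 1:1 allocation, and a fraction of missing information (FMI) equal to the missing fraction, 0.18 (range 0.10 to 0.25).

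**Analytic check, N = 28.**
- Complete-data variance of the adjusted difference: W = 7.89² × (1 − 0.3²) × 4/28 = 62.25 × 0.91 × 0.1429 = 8.09, so SE = 2.84.
- Total variance: T = W/(1 − FMI) = 8.09/0.82 = 9.87, so SE = 3.14.
- Between-imputation variance: B = FMI × T = 0.18 × 9.87 = 1.78, so SD = 1.33.
- Monte Carlo SD of the pooled difference: √(B/m).

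| m | √(B/m), points |
|---|---|
| 5 | 0.60 |
| 18 | 0.31 |
| 50 | 0.19 |
| 100 | 0.13 |

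Over N = 22 to 29, r = 0.2 to 0.4 and FMI = 0.10 to 0.25, the m = 5 value runs from 0.40 to 0.85.

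**Simulation check.** This used a baseline-adjusted linear model, r = 0.3, missing positions chosen at random, 100 imputations in each of 400 datasets, and predictive mean matching with 1, 5 or 10 donors, with and without three extra covariates in the imputation model. Median Monte Carlo SDs were:
- 28 patients, 5 missing: 0.51 to 0.55 at m = 5, and 0.27 to 0.29 at m = 18.
- 22 patients, 4 missing: 0.57 to 0.60 at m = 5, and 0.30 to 0.31 at m = 18.
- Normal-model imputation instead of matching, 28 patients: 0.64 to 0.69 at m = 5.

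**Scale at m = 5.**
- Against the target: 0.51/4 = 13% to 0.60/4 = 15%.
- Against the SE: √(FMI/m) = √(0.18/5) = 0.19. At FMI 0.25 it would be 0.22.
- Relative efficiency: 1/(1 + 0.18/5) = 0.965, against 1/(1 + 0.18/18) = 0.990 at m = 18.
- Pooled SE, √(W + (1 + 1/m)B): √(8.09 + 1.2 × 1.78) = 3.20 at m = 5, and √(8.09 + 1.056 × 1.78) = 3.16 at m = 18, a reduction of about 1.3%.

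**The case against.** The strongest reply is that little depends on this. The total SE is about 3.1 points, so the 95% interval extends more than 6 points either side of the estimate. Rubin's variance already includes the finite-m term, so the interval is valid at m = 5. Moving to 18 narrows it by only about 1%. For a true 4-point effect t is about 4/3.14 = 1.3, and a one-SD change of seed moves it by about 0.19. The SAP repeatedly asks for caution and claims no conclusive evidence (Sections 2, 4.3, 6.7). All of this stands, and it limits the importance of the point. It does not supply a reason for capping m, and wide sampling error is no argument for adding noise that can be removed at no cost.

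A reader might infer several stronger things that the document does not support.
- **That the results are not usefully reproducible.** A Monte Carlo SD under a fifth of the SE does not amount to that.
- **That a small trial needs a large m most.** The noise is larger in raw points when N is small, but relative to the SE it is about √(FMI/m), which does not depend on N.
- **That every secondary outcome is affected to this degree.** Table 2 reports self-harm only descriptively, and no missingness is given for any secondary outcome.
- **That the 18% is known to be interim.** Section 4.6 refers to the current dataset and Section 6.1 plans the last visit for July 2021. That makes a later change possible but does not establish it.
- **That omitting a seed from the SAP is an error.** A seed can be recorded in the analysis code.

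**Conclusion.** The point holds as a departure from the plan's own rule for a reason that does not apply, with a modest consequence. At m = 5 the pooled primary difference carries an avoidable seed-to-seed SD of about 0.5-0.6 ZAN-BPD points, which raising m to 18 roughly halves. This figure is a standard deviation, not a bias or a maximum shift.

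It rests on an assumed analysis set of about 28, an FMI near the missing fraction, and a model without the random site effect of Section 6.7, so it is indicative. It also matters only where imputation is actually run. Section 4.6 says in one paragraph that complete cases will be used if the test supports missing completely at random, and in the next that multiple imputation will be used. If the first governs and the test is passed, m has no bearing on the primary result.

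**What to change.** In Section 4.6, delete the argument that 18 sets are too many for the sample, together with the limit of 5. State instead that, wherever multiple imputation is used, m will be at least the percentage missing at database lock, which is 18 on the current figure. A larger value such as 50 or 100 goes beyond the plan's rule but is preferable, because it brings the Monte Carlo SD down to about 0.19 or 0.13 points. Recording the seed with the analysis code would be good practice. The cost is a one-sentence edit and seconds of computing.
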